All SAE will be reported in due time by the investigator to the sponsor with copy to the trial PI. Then the PI or the sponsor will request a DSMB meeting. The DSMB should give advice to the sponsor about stopping the study (temporarily or permanently) or continuing the study. The following criteria will be considered:

- The study may be stopped if a volunteer within the period 0-28 days after vaccination suffers from clinical whooping cough without laboratory demonstration of wild-type *B. pertussis*. In such a case it must be suspected that the symptoms are caused by BPZE1.
- The study may be stopped if a volunteer has a SAE which is considered by the DSMB to be most probably caused by BPZE1.

II.3. METHOD OF BLINDING AND BREAKING THE STUDY BLIND

The 16 subjects in each dosage group study will be vaccinated in a double-blind manner (active vaccine vs. placebo). That means that all trial participants and all site staff involved in participant recruitment and follow-up will be blinded to treatment assignment. Vaccine and placebo are not distinguishable at the 10^7 dose level when thawed. For higher dose levels (10^8 , 10^9), where vaccine and placebo may be distinguishable when thawed, observer-blinding will be established, by the fact that the vaccine will be prepared and administered by a study nurse not involved in any other trial procedures

Sponsor staff and laboratory staff involved in review/analysis of data are unaware of the treatment assignments. The 6 volunteers with high PRN antibodies in the control group (group 4) will be vaccinated with active vaccine (no blinding, open label).

The information if a vial contains vaccine or placebo will only be available at the statistics center (EUCLID), Lund University Hospital pharmacy (for emergency unblinding), at the manufacturer's site (Q Biologicals) and at the sponsor pharmacovigilance site.

Since access to results of the cultivation of BPZE1 from the nasopharynx samples and the antibody determination may lead to treatment unblinding, these results will be strictly controlled within the respective laboratory. The access of these results outside the laboratory will be contingent on having a previous access to the randomization list and therefore will only be authorized after the completion of

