the study, with the exception a statistician in order to perform an interim analysis after 28-days follow-up. At the end of the trial, the study will be unblinded after all safety and laboratory results are monitored and the data bases are locked.

EXCEPTIONS!

- 1) If any subject has detectable vaccine strain bacteria in the nasopharyngeal sample collected 28 (-1; +7) days after vaccination. Under such a circumstance the laboratory has to inform the investigator, who should arrange for an extra visit for collection of a new nasopharyngeal sample for control of bacterial presence.
- 2) In case of a medical event that investigator/physician in charge of the participant feels cannot be treated without knowing the identity of the study treatment, an emergency unblinding procedure is in place at the Lund University Hospital pharmacy (available 24 hours 7 days a week). If there is a possibility the investigator or delegate should be contacted before the code is broken. The investigator/physician in charge sends a fax of request to the pharmacy, which breaks the code by opening the individual sealed envelope, fills in the unblinding form and faxes the completed form to the investigator/physician in charge. The sponsor should be informed within 24 hours of any unblinding. As far as possible all examinations during study follow-up must be performed on all subjects who received the investigational product.

Unblinded interim reports for the DSMB will be prepared before escalation to the next dose by the trial statistician. An additional interim analysis will be performed when culture results are available from twenty-eight days after vaccination of the high dose group 3. For the latter, another statistician will get access to the randomization list for groups 1-3 to provide a summary of safety and colonization data to the Sponsor/ILiAD for use in discussion with regulatory agencies about a Phase II study. The interim analysis will provide no information about individual volunteers that could reveal the vial codes and the statistician performing the interim analysis will not be involved in any other trial procedure or in the final statistical analyses.

III. Introduction

III.1. BACKGROUND

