In summary this proof-of-concept study showed that the genetically modified strain of *B. pertussis* BPZE1 in humans can colonize the nasopharyngeal mucosa without eliciting any symptoms of mild or severe whooping cough and is otherwise safe and immunogenic. In future trials it will be crucial to ascertain that administration of BPZE1 also in a dosage sufficient to colonize greater than 70 percent of vaccinees still does not cause symptoms of mild or severe whooping cough.

III.3. BENEFIT/RISK AND ETHICAL ASSESSMENT

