XIII. Recording and reporting of Adverse Events Following Immunization

XIII.1. DEFINITIONS

Adverse Event Following Immunization

In this study AEFI are defined according to the current definition generally used in vaccine pharmacovigilance (Report of CIOMS/WHO Working Group on vaccine pharmacovigilance 2012) as: *"any untoward medical occurrence which follows immunization and which does not necessarily have a causal relationship with the usage of the vaccine. The adverse event may be any unfavourable or unintended sign, abnormal laboratory finding, symptom or disease."*

Serious Adverse Event

An AEFI is considered as serious adverse event (SAE) or a serious adverse reaction (SAR)

- results in death;
- is life-threatening (means that the subject was at immediate risk of death at the time of the event; it does not refer to an event which hypothetically might have caused death if it were more severe);
- requires hospitalization or prolongation of existing hospitalization;
- results in persistent or significant disability or incapacity;
- is a congenital anomaly or birth defect;
- is an "important medical event" (medical events, based upon appropriate medical judgment, which may jeopardize the subject or may require medical or surgical intervention to prevent one of the above characteristics/consequences);

Examples: allergic bronchospasm requiring intensive treatment at an emergency room or at home, blood dyscrasias, convulsions that do not result in inpatient hospitalization, suspected transmission of an infectious agent via a medicinal product...

Is a special interest Adverse Event:

- clinical pertussis in a colonized individual if wild type *B. pertussis* is not detected by culture or PCR.

EXCEPTIONS: SAE not requiring immediate reporting to the sponsor

- Medical or surgical procedures (e.g.: surgery, endoscopy, tooth extraction, transfusion); only the condition that leads to the procedure should be notified if the condition is referring to a seriousness criteria described above.
- Pre-existing diseases or present conditions or detected prior to start of study drug administration that do not worsen.
- Situations where an untoward medical occurrence has not occurred (e.g.: hospitalization for elective surgery if known prior to start study, social and/or convenience admissions, pre-specified study hospitalizations for observation).

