- The study may be stopped if a volunteer within the period 0-28 days after vaccination suffers from clinical whooping cough without laboratory demonstration of wild-type *B. pertussis*. In such a case it must be suspected that the symptoms are caused by BPZE1.
- The study may be stopped if a volunteer has a SAE which is considered by the DSMB to be most probably caused by BPZE1.

At the regular DSMB meetings before the start of dose group 2 and 3, respectively, the DSMB will review all accumulated safety data in the trial (AEs and SAEs per dose and randomized allocation) and make a recommendation whether the next higher dose can be administered.

A DSMB charter will describe the functioning of the DSMB.

XIV. Endpoints

XIV.1. PRIMARY SAFETY ENDPOINT

The primary safety endpoint will be the number and proportion of participants, per dose group and randomized allocation, with at least one of the following adverse events between Day 0 (Visit 2) and Day 28 (Visit 8):

- Cough and spasmodic cough of grade 2 or higher.
- Other respiratory tract AE related or possibly related to vaccination of grade 3 or higher.
- Any other AE related or possibly related to vaccination of grade 3 or higher.

XIV.2. SECONDARY SAFETY ENDPOINT

The second safety endpoint will be the number and proportion of participants per dose group and randomized allocation, with:

- at least one episode of cough or spasmodic cough, described by grade, between Day 4 and Day 28
- at least one solicited or unsolicited AEFI from respiratory tract between Day 0 and Day 28
- at least one AEFI with difficulties in breathing (asthma, spasmodic cough, pneumonia) between Day 0 and Day 28
- at least one other AEFI from the respiratory tract between Day 0 and Day 28
- at least one episode of cough, described by grade, between Day 0 and Day 28
- at least one episode of spasmodic cough, described by grade, between Day 0 and Day 28
- at least one solicited systemic AEFI between Day 0 and Day 28 (fever, headache, tiredness)
- at least one unsolicited AEFI between Day 0 and Day 28

Adverse events following immunization (AEFI) should be reported at study visits during the first 28 days of the concerned subject.

Serious adverse events (SAE) should be reported immediately but no later than 24 hours after detection. AEFI which lead to difficulties in breathing (asthma, spasmodic cough, pneumonia) will be considered as serious and reported to the Data Safety Monitoring Board (DSMB) and the sponsor.

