Since access to results of the cultivation of BPZE1 from the nasopharynx samples and the antibody determination may lead to treatment unblinding, these results will be strictly controlled within the respective laboratory. The access of these results outside the laboratory will be contingent on having a previous access to the randomization list and therefore will only be authorized after the completion of the study, with the exception a statistician in order to perform an interim analysis after 28-days follow-up. At the end of the trial, the study will be unblinded after all safety and laboratory results from 6 months follow up are monitored and the data bases are locked. The volunteers will be blinded until after the 12 month-follow up.

Unblinded interim reports for the DSMB will be prepared before escalation to the next dose by the trial statistician. An additional interim analysis will be performed when culture results are available from twenty-eight days after vaccination of the high dose group 3 and 4, respectively. For the latter, another statistician will get access to the randomization list for groups 1-3 to provide a summary of safety and colonization data to the Sponsor/ILiAD for use in discussion with regulatory agencies about a Phase II study. The interim analysis will provide no information about individual volunteers that could reveal the vial codes and the statistician performing the interim analysis will not be involved in any other trial procedure or in the final statistical analyses.

A clinical study report containing data of the primary and secondary end-points will be prepared when the safety and laboratory results from 6 months follow up are monitored and the data bases are locked. A separate report will be prepared containing the results of the 12 months follow up.

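### Pertussis in a colonised volunteer cannot be classified as the protocol defines it before Day 28, and the DSMB's escalation reports carry no colonisation data

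*Combined protocol and SAP*

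**What the plan says.** **The lock.** Protocol II.3 recognises that BPZE1 cultures and antibody levels can reveal allocation, and so "these results will be strictly controlled within the respective laboratory". It continues: "The access of these results outside the laboratory will be contingent on having a previous access to the randomization list". SAP 1.4 repeats the rule: release "will only be authorized after the completion of the study, with the exception a statistician in order to perform an interim analysis".

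**The exceptions.** Protocol II.3 gives three routes.
- The laboratory tells the investigator of a positive Day 28 culture, so that an extra visit can be arranged.
- Emergency code-breaking through the pharmacy discloses the treatment.
- One statistician has access, "with the exception a statistician in order to perform an interim analysis after 28-days follow-up". II.3, XV.2.3 and SAP 2.1.6 describe this as a separate analysis after Day 28 of group 3, done by someone with no other trial role, for the sponsor/ILiAD.

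**What depends on laboratory results.** Protocol XIII.1 lists as a special-interest serious event "clinical pertussis in a colonized individual if wild type" *B. pertussis* is not found by culture or PCR. Stopping criterion 1 (II.2, XIII.7) applies if a volunteer in the first 28 days "suffers from clinical whooping cough without laboratory demonstration of wild-type" *B. pertussis*.

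**What the DSMB sees.** Under XIII.7, before groups 2 and 3 start, "the DSMB will review all accumulated safety data in the trial (AEs and SAEs per dose and randomized allocation"). SAP 3.10 itemises the report down to work accidents but has no culture or colonisation entry. SAP 3.11 does plan respiratory symptoms by colonised and non-colonised, but only in the analysis after group 3.

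**The concern.** Protocol III.2 states the safety question in terms of colonisation: it must be shown that BPZE1 "in a dosage sufficient to colonize greater than 70 percent of vaccinees still does not cause symptoms of mild or severe whooping cough". The earlier trial found colonisation to be dose-dependent, and only culture-positive subjects had antibody rises. A volunteer who is not colonised therefore says little about whether colonisation causes pertussis symptoms.

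Two things are at stake. First, the investigator must report a serious event within 24 hours, but one of the defined serious events turns on a fact that the blinding rule withholds from both the investigator and the DSMB. Second, the DSMB advises on each ten-fold step without knowing how many of the 12 vaccinees carried the organism, so it cannot judge how informative a clean safety table is.

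**Working it through.** **1. The plan's own figures (Protocol XV.1, SAP 1.3).** All three reproduce.
- Chance of at least one event in 12 at a 12.6% rate: 1 − (1 − 0.126)^12 = 80.1% (stated 80%).
- Two-sided 95% exact upper bound for zero events, 1 − 0.025^(1/n): n = 12 gives 26.5% (stated 26%); n = 36 gives 9.7% (stated 10%).

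**2. Who can learn colonised status, and when.**

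| Route | What it discloses | To whom | Serves a case before Day 28? |
|---|---|---|---|
| Positive Day 28 culture | Colonised at that visit | Investigator | No |
| Emergency code-break | Allocation, not culture | Treating physician | No |
| Interim statistician | Summary colonisation data after group 3 | Sponsor/ILiAD | No |
| DSMB escalation report | AEs and SAEs by arm | DSMB | No culture item listed |

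The first route also covers only volunteers still positive at Day 28. One who was positive earlier and had cleared by then is not disclosed. The third route comes after both escalations.

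**3. Which rules need a BPZE1 culture.**
- Special-interest event (XIII.1): yes, because colonised status is part of the definition.
- Stopping criterion 1: no. It needs whooping cough and no demonstrated wild type.
- Stopping criterion 2: not formally. It is a DSMB judgement on whether BPZE1 most probably caused an SAE, although recovery of BPZE1 is obvious evidence for that judgement.
- Ad hoc DSMB meeting (XIII.7): no. Any SAE triggers it, including AEFIs with breathing difficulty such as spasmodic cough.

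**4. What the missing colonisation count hides.** The number colonised among 12 at each dose is unknown, so the counts below are assumptions. Five repeats the 5/12 seen at 10^7 cfu in the earlier trial (III.2). Nine is the smallest count above 70%, since 8/12 = 66.7% and 9/12 = 75%.

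| Colonised of 12 | Upper bound if 0 events, 1 − 0.025^(1/n) | Chance of ≥1 event at a 12.6% rate, 1 − 0.874^n |
|---|---|---|
| 5 | 52.2% | 49.0% |
| 9 | 33.6% | 70.2% |
| 12 | 26.5% | 80.1% |

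The earlier rate does not settle which row applies: the exact 95% interval for 5/12 runs from 15.2% to 72.3%.

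**The case against.** A reader might infer that the stopping criteria cannot be applied at all. The documents do not support that.
- Criterion 1 does not mention BPZE1 culture. If no wild type is shown the criterion is met, and the protocol then directs suspicion to the vaccine, so missing data lean towards caution.
- The criteria are non-binding guidance.
- Spasmodic cough and other breathing-difficulty events count as serious and reach the DSMB on symptoms alone, whatever the culture shows. A symptomatic case would be detected and reviewed.

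Nor is the lock absolute until study end, given the Day 28 and interim-statistician exceptions. It names BPZE1 cultures and antibodies, not wild-type results, so nothing forbids releasing the latter. The statistician exception could also be read as covering the DSMB reports, since XV.2.3 lists both under interim analyses. The DSMB charter and Laboratory analytical plan are not among the documents and may deal with access.

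The illustration can also be challenged. The 5/12 comes from men aged 21–28, and the culture-negative high-dose subjects had higher PRN antibodies. Groups 1–3 here exclude PT or PRN of 20 IU/ml and above, so colonisation may differ. A review of safety per administered dose is also coherent in itself, and symptoms by colonisation status are planned for the final analysis.

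Most of this stands, and it limits the point to the special-interest definition and the content of the escalation reports. It does not remove either. The text ties colonisation access to the separate statistician after group 3, and an unseen charter cannot be assumed to override an access rule stated in both protocol and SAP. A final analysis comes too late for escalation. On wild type, the documents give no route for obtaining or releasing a result, and PCR appears in no laboratory or sampling table (XII.1, XII.3, XII.4).

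**Conclusion.** The point holds in this limited form. Protocol XIII.1 conflicts with II.3 and SAP 1.4: a defined serious event cannot be classified as written before Day 28. Separately, the DSMB's planned reports would not show whether 0/12 (upper bound 26.5%) is backed by few colonised vaccinees (52% for 5) or many (34% for 9). Those two bounds rest on assumed colonisation counts and serve as a range, not a forecast. The conclusion rests on the visible protocol and SAP; a charter or laboratory plan that already provides access would reduce the work to a cross-reference. This is a cheap and worthwhile improvement. It is not evidence that the stopping criteria or symptom-based DSMB review would fail.

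**What to change.** Reconcile Protocol II.3 and SAP 1.4 with Protocol XIII.1 and XIII.7 and SAP 3.10.

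1. Add a firewalled exception to II.3 and SAP 1.4. The laboratory releases BPZE1 culture results, and any wild-type results, to the DSMB through the EUCLID statistician who prepares its unblinded reports. For this purpose nothing goes to the site or sponsor. State that it applies both to a suspected case as it arises and to each escalation report.
2. In XIII.1, say who assigns the special-interest label, given that the site stays blind to culture. State how a wild-type result is obtained and released for DSMB review.
3. Add to SAP 3.10, per arm: culture positivity by visit, and the primary endpoint by colonised/not colonised.

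The stopping criteria and all clinical rules stay unchanged.

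**Cost.** Wording in two documents and a small addition to the DSMB report. The laboratory must release results cohort by cohort to one statistician who is already unblinded. EUCLID already holds the randomisation list, so this fits II.3's own access condition and leaves site and sponsor blinding intact. The timing looks feasible: the Day 28 exception already assumes cultures are read in time to book the Day 45 visit, and at least six weeks of follow-up precede the next group's vaccination.
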